The primary objective of this proposal is to identifying the neurobiologic substrates of emotion-related behavior in CD individuals. After the initial screening and assessment visit, an fMRI study visit will be scheduled (Figure 4). The study will use a double-blind placebo-controlled design. Prior to the scan, participants will receive either intranasal OT (24 IU) or a placebo (PBO) spray. During the scan, BOLD fMRI data will be acquired while the participants perform a series of stressful and non-stressful mental arithmetic challenges (Dedovic et al., 2005). Performance feedback will be provided by the MIST software in real-time and also by the investigator. Participants will complete three runs of the MIST. Subjective responses (anxiety and craving) will be collected at baseline and immediately after each run of the MIST. Participants will also complete an implicit facial affect recognition task. Since the amygdala may habituate to the stress tasks, the order of the tasks will be counterbalanced. At the end of the study visit, subjects will be debriefed, compensated and discharged.

C3b. Participants

Subjects will be men and women of all racial and ethnic groups aged 18-65. A total of 160 study participants will be recruited: (1) cocaine-dependent individuals (CD, n=80); and (2) healthy control subjects free of major Axis I diagnoses (HC, n=80). Gender differences in the neural correlates of stress have been found in fMRI studies of HC and CD individuals (Li et al., 2005; Potenza et al., 2012), and in amygdala responses to fearful faces following intranasal OT administration (Domes, Heinrichs, Glascher, et al., 2007; Domes et al., 2010). Based on our experience in recruiting CD subjects for clinical studies, we expect that 15-20% of the subjects will be female. Differential recruitment will be used as needed to ensure that 15-20% of the participants in each study

group are female. Groups will also be matched on age, smoking status, and education. On a monthly basis, we will assess the status of each group in terms of core variables and tailor recruitment

Figure 4. Overview of Study Visit Procedures

accordingly. This has worked well in all of our previous clinical research studies.

C3c. Recruitment and Retention

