Intranasal OT and matching PBO (saline spray) will be compounded by MUSC's Investigational Drug Services (IDS) which has extensive experience in extemporaneous OT preparation and quality control monitoring. Randomization will be done by IDS, who will keep a record of the blind. The record will be available should unblinding be required. To achieve balance in sample size with respect to gender, smoking status, and age, a block randomized design with randomly varying block sizes will be used. OT or PBO sprays will be administered at the CBI and under the supervision of the study staff approximately 45-minutes prior to the scanning session. First the participant will be asked to blow their nose. The vial will be primed to ensure that each puff contains OT or placebo spray and not air. The participant will be instructed to exhale through their nose and then spray into one nostril while inhaling. Nostrils will be alternated and the participant will be asked to repeat the procedure for each nostril. Participants will self-administer nasal spray in each nostril until a total of 24 IU is reached. The number of puffs will vary depending on the strength of the oxytocin; IDS provides this information. This dose and timing of administration were selected based on similar fMRI studies demonstrating BOLD signal changes in the amygdala 45-50 minutes post-administration (Domes, Heinrichs, Glascher, et al., 2007; Domes et al., 2010; Kirsch et al., 2005; Labuschagne et al., 2010).

MRI Data Acquisition

All MRI data will be acquired on a Siemens Trio 3T scanner (Siemens Medical, Erlangen, Germany). Participants will be placed in the mock scanner to acclimate to the scanning environment. If the mock scanner is not available on the test day, participants will proceed directly to the actual scan. Participants will be screened for metal using a handheld metal detector. Study personnel will position subjects on the scanner bed with foam padding placed around their head to prevent motion. Participants will wear earplugs/headphones and the task will be projected on a wide screen located at the end of the scanner bore and viewed via a back-projected mirror that will be mounted on 12-channel head coil. Participants will use a non-ferrous optical hand pad to submit their answers to the arithmetic task. The hand pad will be connected via an optical cable to a computer outside

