The study will use a block design of three, six-minute runs separated by two-minutes of rest for feedback, for a total of 24-minutes. During each run, participants will be exposed to 40-second blocks of three different conditions (rest, control, and stress). Prior to the task, a research assistant will meet with each participant and described the parameters of the task. The participants will be shown images of what the screen will look like during each condition. The participants will be instructed to relax during the rest condition and focus on the screen. During the control condition, the participants will be asked to answer math problems as accurately as possible but will also be told that their responses will not be recorded. During the stress condition, the participants will be asked to perform the math task as quickly and accurately as possible. They will be given immediate feedback about their performance and will be able to see the performance level of an “average” person through a performance bar that will be located at the top of the screen. A strict time limit will be enforced throughout the stress condition. The participants will be told that the average person would answer about 85% of the questions correctly, while in reality, the program’s algorithm limits the participants’ performance rate to between 35-45%. At the end of runs one and two, the participants will be given negative feedback from the investigator and will be urged to improve their performance so that their data may be included in the study. To minimize the effects of scanner drift, the beginning condition will be counterbalanced between participants. However, the sequence of conditions will be constant (i.e. control condition will follow the rest condition and the stress condition will follow the control condition).

Implicit Facial Affect Recognition Task

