Preprocessing: Post-acquisition preprocessing and statistical analysis of all of the neuroimaging data will be performed using FEAT (FMRI Expert Analysis Tool) Version 5.98, part of FSL (FMRIB's Software Library, www.fmrib.ox.ac.uk/fsl). Functional magnetic resonance imaging (fMRI) blood oxygen level dependent (BOLD) imaging data will be acquired using a standard multi-slice gradient echo planar imaging sequence (TR=2200 ms, TE=35 ms, 64 x 64 matrix, 3 mm isotropic voxels, 271 volumes). Data will be preprocessed using scripting tools from FMRI Expert Analysis Tool (FEAT) Version 5.98, part of FMRIB's Software Library (FSL; www.fmrib.ox.ac.uk/fsl). First non-brain signal will be removed using FSL's BET brain extraction. Scans will be corrected for motion using FSL's linear registration and scans will be spatially smoothed using a Gaussian kernel of 8 mm FWHM. Since head motion can impact functional connectivity analyses, participants with head motion exceeding 0.2 mm will be excluded from the analyses (Power et al., 2012). The "fsl_motion_correction" scripting tool will be used to identify and scrub motion artifacts from each participant's data (Power et al., 2013). Scans will be spatially co-registered with a standardized anatomical template (Montreal Neurological Institute) using a 12 parameter affine transformation (Rorden et al., 2000). **Analysis:** Functional connectivity will be measured using a PPI based approach (Friston et al., 1997). A customized square wave form representing the task (1 = stress condition and -1 = control condition) and the duration of each condition will be convolved with a double-gamma hemodynamic response function. A mask of the seed region will be made using a 12-mm diameter sphere located in the center of the left amygdala using the MNI coordinates (x, y, z = -22, 0, -22). The transformation parameters described above will also be applied to the mask. For each participant and each run of the MIST, the mean corrected and high pass filtered time series of the BOLD signal in the left amygdala will be extracted and used in a single subject whole brain PPI analysis. The PPI model will include (1) the task vector; (2) the time series of the BOLD signal in the left amygdala; (3) a term representing the positive task x seed interaction; and (4) a term representing the negative task x seed interaction. The first level analysis will generate contrast images of the parameter estimates for each of the four regressors. Since the hypotheses associated with Specific Aim 1 explore increases in amygdala - prefrontal cortical connectivity in response to social stress, the group analysis will focus on the positive interaction term. The contrast images of the parameter estimates of the positive interaction term will be entered into a 2nd-level random effects analysis. Unpaired t-tests will be used to test for the following group differences (Hypothesis 1A: CD-PBO vs. HC-PBO) and (Hypothesis 1B: CD-OT vs. CD-PBO). Analyses will be conducted using FMRIBs Local Analysis of Mixed Effects (FLAME 1). Additional analyses comparing (HC-OT vs. CD-OT) will be conducted using an unpaired t-test and applying the appropriate corrections for multiple tests. We will also conduct an exploratory gender analysis between the CD and HC women in the four groups (Domes, Heinrichs, Glascher, et al., 2007; Domes et al., 2010; Potenza et al., 2012). We anticipate that 15-20% of the subjects in each group will be female (n=6/8 per group). We

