
acknowledge that we may be underpowered to conduct these tests. Since there may be important group differences in regional brain activity during the MIST, a secondary whole brain analysis will be conducted using the contrast of interest (stress-control). Analyses will be conducted using FMRIBs Local Analysis of Mixed Effects (FLAME 1). All group level results will be thresholded at $Z>2.3$ using a corrected cluster threshold of $p=0.05$.

Hypothesis 1C: The CD-OT group will report lower subjective anxiety and craving than the CD-PBO group.

Analysis: A linear mixed effects model containing all serially measured time points will be used to assess the effects of OT versus placebo on each dependent variable. Restricted maximum likelihood (REML; Patterson and Thompson, 1971) methods will be used to estimate the fixed effects and variance components, and baseline values will be used as covariates in the regression models. The dependent variables anxiety and craving will be modeled separately. Within each family of dependent measures, the Type I error rate will be controlled using a post-hoc Bonferroni correction. The statistical analyses will be conducted using SAS 9.3 software (SAS Institute Inc., Cary, NC, USA).

Specific Aim 2: Use an implicit facial affect recognition paradigm to determine the impact of cocaine dependence and oxytocin on amygdala activity in response to fearful faces.

Hypothesis 2A: The CD-PBO group will exhibit greater amygdala activity in response to fearful faces than HC-PBO group.

Hypothesis 2B: Compared with the CD-PBO group, participants in the CD-OT group will exhibit lower amygdala activity in response to fearful faces.

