Data Analysis: Following preprocessing (described above), within-task data from individual participants will be analyzed with a fixed-effects general linear model (GLM), with each emotion (described below) modeled as a box-car function convolved with a double-gamma hemodynamic response function. The response period at the end of each block will also be modeled as a separate variable to remove effects of explicit decision making and response selection. The GLM procedure is repeated for each voxel with six movement parameters (3 rotation values in radian and 3 translation values in millimeter) included as covariates to control for the influence of head motion on the data. Following first-level analysis, subject-specific contrasts will be entered into second-level, random-effects analyses. Since the hypotheses associated with Specific Aim 2 explore amygdala activity, we will use a region of interest approach (ROI). The BOLD signal from the left amygdala will be extracted using an anatomical mask generated by a 12-mm diameter sphere located in the center of the left amygdala using the MNI coordinates (x, y, z = -22, 0, -22). The percent signal change between the fearful and neutral conditions (contrast of interest) will be calculated for each participant. Separate random-effects one-way analysis of variance tests (ANOVA) will be used to test for the following group differences (Hypothesis 2A: CD-PBO vs. HC-PBO) and (Hypothesis 2B: CD-PBO vs. CD-OT). Since human neuroimaging studies have found that other brain regions play a role in implicit emotional processing, including the right amygdala and insula (Davidson et al., 1999; Shi et al., 2013), secondary analyses will also include these regions. In addition, OT may impact amygdala responding to happy faces (Domes, Heinrichs, Glascher, et al., 2007), therefore group differences in amygdala responding in the happy-neutral contrast may be explored in future analyses. For multiple comparisons that are not part of the hypothesis a priori, the Bonferroni correction will be used. In addition, contrasts of other pertinent baseline characteristics will be performed between groups. If the groups differ significantly on any of these baseline characteristics, the corresponding variables will be used as covariates in the above analyses. The statistical analyses will be conducted using SAS 9.3 software (SAS Institute Inc., Cary, NC, USA).

Power and Sample Size

Specific Aim 1

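### Task order and the factors balanced at randomisation are left out of the group models, which costs some precision and leaves chance imbalance uncorrected; prespecified adjustment is nearly free

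*Combined protocol and SAP*

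**What the plan says.** C3a Overview gives both the design feature and its reason: "Since the amygdala may habituate to the stress tasks, the order of the tasks will be counterbalanced". The Specific Aims page also says that task order is counterbalanced. Neither place says that this is done within each of the four groups (cocaine-dependent or healthy control, oxytocin or placebo).

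Medication Administration describes the randomisation method adopted: "To achieve balance in sample size with respect to gender, smoking status, and age, a block randomized design with randomly varying block sizes will be" [...]. Task order is not one of its balancing factors.

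C3f Statistical Methods then sets out these analyses:

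- **1A and 1B, first level:** "The PPI model will include (1) the task vector; (2) the time series of the BOLD signal in the left amygdala", plus a positive and a negative interaction term.
- **1A and 1B, group level:** "Unpaired t-tests will be used to test for the following group differences". No covariate is named.
- **Secondary analysis of the stress task:** "a secondary whole brain analysis will be conducted using the contrast of interest (stress-control"). No covariate is named.
- **1C:** a linear mixed model for anxiety and for craving, with the baseline value as the only named covariate.
- **2A and 2B:** six movement parameters at first level, then "Separate random-effects one-way analysis of variance tests (ANOVA) will be used to test for the following group differences".

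The closing rule of the Aim 2 analysis brings in baseline characteristics as covariates only where the groups differ significantly on them. The further provisions in C3e Assessments (nicotine withdrawal) and C3g Design Considerations (childhood trauma, drug-use pattern) also concern participant characteristics and are optional or conditional. Task order is a design factor and falls under none of these rules.

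**The concern.** The plan names a reason why order could matter and controls it by design, but then analyses the data as if order did not exist. The left amygdala is both the seed for Aim 1 and the region of interest for Aim 2, so any habituation would act on the measured quantity. A balanced factor that is left out of the model puts its variance into the residual. If balance is lost after scanning, for instance through the exclusion of participants with head motion above 0.2 mm, part of the order effect can also move into the group difference with nothing to remove it.

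Gender, smoking status and age raise the same question. The plan considers them important enough to balance, yet their use in the analysis depends on a significance test of baseline differences. Such a test says nothing about how strongly a factor predicts the outcome.

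Order also changes how long after dosing each task is performed. That bears on the oxytocin comparisons, and most of all on 2B.

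**Working it through.** **Inputs from the documents.** 40 per group; d = 0.9 for 1A and 1B (difference 3.6, RMSE 4.0); effect size 1.2 for Aim 2; type I error 0.05, taken as two-sided. The stress task lasts 24 min. The face task has 6 task blocks of 27.5 s plus a 5 s response, and 7 rest blocks of 27.5 s.

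**Input not in the documents.** The size of the order effect, *o*, in within-order SDs of the within-task contrast. Assumed range: 0.3 to 0.8.

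**The plan's own power figures.** For d = 0.9, 80% power needs 2(1.960 + 0.842)²/0.9² = 19.4, so 20 per group (21 by noncentral t). The stated 40 per group therefore gives power 0.978. The gap between 40 and 20 to 21 is a separate matter, relevant here only as headroom. For Aim 2, reading 1.2 as a standardised mean difference with 19 per group gives 0.949 to 0.959, which reproduces the stated .95. At 40 per group, power is about 1.00.

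**Residual variance.** A 50:50 factor with effect *o* multiplies the within-group variance by 1 + o²/4. Its share of that variance is R² = (o²/4)/(1 + o²/4).

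| o (assumed) | Variance factor | R² | Equivalent n of 40 | Loss |
|---|---|---|---|---|
| 0.3 | 1.0225 | 0.022 | 39.1 | 0.9 |
| 0.5 | 1.0625 | 0.059 | 37.6 | 2.4 |
| 0.8 | 1.16 | 0.138 | 34.5 | 5.5 |

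**Power with order in the model.** 40 per group, residual SD multiplied by √(1 − R²), one error df lost, and all order variance counted as noise in the unadjusted test. The R² values 0.05, 0.10 and 0.20 correspond to *o* of about 0.46, 0.67 and 1.0, so the last lies beyond the range above.

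| d | Order omitted | R² 0.05 | R² 0.10 | R² 0.20 |
|---|---|---|---|---|
| 0.9 (1A, 1B) | 0.978 | 0.983 | 0.987 | 0.993 |
| 1.2 (Aim 2) | about 1.00 | about 1.00 | about 1.00 | about 1.00 |
| 0.635 (80% power at n = 40) | 0.80 | 0.82 | 0.84 | 0.88 |

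The gain is 0.5 to 1.5 points at d = 0.9. It reaches 2 to 8 points only at d = 0.635, which is not a planned effect. If order has no effect, modelling it costs less than 0.1 point.

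**Type I error of the unadjusted t-test (simulated).** With order exactly balanced in both groups: 0.044, 0.040 and 0.027 at R² of 0.05, 0.10 and 0.20. With order left to chance: about 0.05.

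**Chance imbalance.** If one group ends with a 60/40 order split and the other with 40/60, the group difference shifts by (0.60 − 0.40) × o. That is 0.06, 0.10 or 0.16 within-order SD for *o* of 0.3, 0.5 or 0.8.

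**Shift in time since dosing.** Faces second rather than first: later by the stated 24 min of the stress task. Stress task second rather than first: later by 6 × 32.5 s + 7 × 27.5 s = 387.5 s, about 6.5 min (somewhat longer if neutral blocks are added to the six listed).

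**Cost in degrees of freedom.** A pairwise imaging comparison has at most 40 + 40 − 2 = 78 error df. Order, gender, smoking status and age (linear) use 4, leaving 74.

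**The case against.** The strongest reply is that counterbalancing is itself a recognised control, that the protocol says only that habituation may occur, and that leaving order out does not invalidate a test. All of this stands: simulated type I error is at or below nominal.

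The outcomes are also within-task contrasts: stress against control, and fearful minus neutral. Habituation that lowers both conditions equally cancels, so only an order effect on the contrast itself enters the residual. No document suggests how large that would be, and 0.8 SD is close to the planned group effect of 0.9.

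Several stronger readings are tempting but unsupported:

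- **That the comparisons are biased.** Bias needs an imbalance in order between the groups. Motion exclusions could cause one, but nothing shows that they will. Drop-out is a weaker route, since there is one scanning session and the plan over-enrols to reach 160 scans.
- **That every imaging comparison suffers alike.** The dosing-time shift is about 24 min for the face task but only about 6.5 min for the stress task.
- **That order pushes the face task outside the 45 to 50 min post-dose period cited for timing.** Assigning exact post-dose start times means assuming that the relaxing pictures (20 × 30 s = 10 min) measure the length of the preliminary scans, which MRI Data Acquisition does not say. On that assumption even the first task would start at about 45 + 10 = 55 min, so the gap would not be caused by order.
- **That an order covariate settles the dosing-time question.** It removes an average shift only. An oxytocin effect that varies with order needs an interaction term.

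Gender, smoking status and age are already handled by recruitment, matching and blocked randomisation, and the magnitudes above say nothing about them. None of this shows a drawback to prespecified adjustment.

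**Conclusion.** The point holds as a low-cost improvement, not as an error that threatens the conclusions. The group models for 1A to 1C and 2A to 2B omit task order and the three factors balanced at randomisation, and baseline adjustment is conditional on a significance test.

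The consequence is lost precision, and no correction for chance imbalance in order after motion exclusions. The size rests on an assumed order effect of 0.3 to 0.8 SD on the within-task contrast: 2% to 16% more residual variance, or about 1 to 6 of 40 participants per group. At the planned effects of 0.9 and 1.2 the loss of power is small, because 40 per group is generous for them. It would matter more if the true effects were smaller. Concern is greatest for the face task, and within it for the oxytocin comparison in 2B, where order and time since dosing move together.

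**What to change.** Make three changes in C3f Statistical Methods, with a matching sentence in C3a Overview:

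1. State that task order is counterbalanced within each of the four groups.
2. Include task order, gender, smoking status and age as prespecified fixed covariates in the group models for 1A to 1C and 2A to 2B, whether or not the groups differ significantly on them. The t-tests and one-way ANOVAs become linear models with a group term, and the covariates are added to the mixed model for 1C.
3. For 2B, report an order-by-treatment check as a sensitivity analysis. It will have limited power and should be labelled accordingly.

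The cost is a few lines of text and about 4 of at most 78 error df per pairwise comparison, fewer than 78 after motion exclusions. The design already generates or uses all four factors, so no new data are needed. The order in which each participant actually did the tasks should be kept in the analysis dataset.

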the scanner room. Their ability to view the projection screen and use of the hand pad will be assessed prior to scanning. During initial scanner tuning, localizing, and structural scanning, participants will be shown “relaxing” images (i.e., 20 scenic pictures, each displayed for 30 seconds). A high resolution T1-weighted MPRAGE anatomical scan (TR = 8.1 ms, TE = 3.7 ms, flip angle = 8°, field of view = 256 mm, 1.0 mm) covering the entire brain and positioned using a sagittal scout image will be acquired for co-registration and normalization of functional images. T2*-weighted gradient echo EPI images will be acquired with the following parameters: TR = 2500 ms, TE = 27 ms, flip angle = 77°, 40 axial slices (FOV = 224 x 224 mm, thickness = 3.5 mm voxels with 0.5 mm gap, in interleaved order. The scanning planes will be oriented parallel to the anterior commissure–posterior commissure line.

The Montreal Imaging Stress Task

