The amygdala response to emotional faces that are presented outside the focus of attention (i.e. implicit tasks) is significantly greater than that observed during overt (explicit) presentation of the same stimuli (Critchley et al., 2000). Emotional adult faces will be selected from a variety of sources are standardized in size and enclosed in the same oval surround (Ekman, 1976). [name] (Co-I) has developed a corpus of faces for a recent project (National Institute of Mental Health, R21 MH086958-01, “A comparative developmental connectivity study of face processing”) that will be used for the present project. The faces will depict male and female Caucasian, Asian and African Americans expressing three different categories of emotion; fear, anger, and happiness. Neutral faces will also be presented (Figure 5). Because the participants will also be from different ethnic categories, it is important to include a mixture of races. In a block design, participants will view a series of faces (for 27.5 sec) within a block and report on the gender of those faces at the end of the block (for 5 sec). Each block will present 56 faces that depict the same emotion and same gender so there will be 6 pseudorandomly ordered task blocks (3 emotions x 2 genders) and 7 rest blocks (27.5 sec each) that present a crosshair to be fixated. In each task block, each emotional face will be presented for 33 msec. followed by a neutral face mask (from a different individual) for 167 msec. followed by a blank screen for 291 msec. At the end of the block participants will report the gender using two buttons on a response pad. Assignment of face sets to sessions will be counterbalanced across subjects.

Payment to Participants

Subjects will be paid with Greenphire debit cards or cash for each completed study visit as follows: \$75 for completing baseline assessments to see if you meet study requirements (\$25 for the physical exam and \$50 for the interview) and \$150 for completing the scanning session. The total amount that they may receive for participating in the study if they complete all study visits is a maximum of \$225. If subjects choose not to complete the study, they will be compensated for the part(s) they have completed. Subjects who come to their

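### The spray timing is justified by amygdala effects at 45-50 minutes, but the schedule puts most or all task data later, and the oxytocin analyses ignore task order and time since dose

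*Combined protocol and SAP*

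**What the plan says.** Medication Administration has the spray given "under the supervision of the study staff approximately 45-minutes prior to the scanning session". The same paragraph supplies the reason: "This dose and timing of administration were selected based on similar fMRI studies demonstrating BOLD signal changes in the amygdala 45-50 minutes post-administration".

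MRI Data Acquisition describes what happens in the scanner before any task: "During initial scanner tuning, localizing, and structural scanning, participants will be shown “relaxing” images (i.e., 20 scenic pictures, each displayed for 30 seconds". The anatomical T1 scan (MPRAGE) belongs to this phase and serves co-registration and normalisation of the functional images.

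The MIST section describes "three, six-minute runs separated by two-minutes of rest for feedback, for a total of 24-minutes". In the Implicit Facial Affect Recognition Task section, "participants will view a series of faces (for 27.5 sec) within a block and report on the gender of those faces at the end" of each block, with 5 seconds allowed for that report. The design there is "6 pseudorandomly ordered task blocks (3 emotions x 2 genders) and 7 rest blocks (27.5 sec each", the rest blocks showing a fixation cross.

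The Specific Aims and section C3a say that the order of the two tasks is counterbalanced; C3a gives amygdala habituation as the reason. In Statistical Methods (C3f), Hypothesis 1B is tested by an unpaired t-test on the connectivity estimates and Hypothesis 2B by a one-way ANOVA on left-amygdala signal change. The covariates foreseen are baseline characteristics on which the groups differ. Neither task order nor time since the spray appears.

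**The concern.** Hypotheses 1B and 2B are the randomised imaging comparisons: oxytocin against placebo in cocaine-dependent participants after a single dose. The reference to 45-50 minutes is the plan's only stated reason for when to scan. That reason concerns a brain response, but the interval runs to the opening of a session that begins with about ten minutes of non-task scanning. If the two do not line up, the plan's own rationale does not cover the data that test these hypotheses, and timing would remain an unexamined explanation for a null result.

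Counterbalancing adds a second layer. The face task is the only source of data for 2B and is short, while the MIST is long. Which task comes first therefore shifts the face task's time since dose substantially. Order is known for every participant, yet the planned models leave whatever variation it causes in the residual.

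**Working it through.** **Inputs**

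- Spray to scanning session: about 45 min (Medication Administration).
- Pre-task scanning: "20 scenic pictures, each displayed for 30 seconds" (MRI Data Acquisition).
- MIST: 24 min in total (MIST section).
- Face task: 6 blocks of 27.5 s viewing plus 5 s response, and 7 rest blocks of 27.5 s (face task section).
- Task order: either task may be first (C3a).
- Mock scanner, positioning and gaps between tasks: no durations given, counted as 0.

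**Reproducing the plan's figures**

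- MIST: 3 × (6 + 2) = 24 min, the stated total, with one two-minute period per run. With only two gaps between three runs it would be 3 × 6 + 2 × 2 = 22 min.
- Face block: 56 × (33 + 167 + 291) ms = 27.5 s, as stated.

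**Timeline, nominal reading**

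- Pre-task scanning: 20 × 30 s = 10 min.
- Face task: [6 × (27.5 + 5) + 7 × 27.5] / 60 = 387.5 / 60 = 6.46 min.
- First functional data: 45 + 10 = 55 min.
- Last functional data: 55 + 24 + 6.46 = 85.5 min.

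| Order | First task | Second task |
|---|---|---|
| MIST first | MIST 55-79 | faces 79-85.5 |
| Faces first | faces 55-61.5 | MIST 61.5-85.5 |

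Face-task onset differs by 79 − 55 = 24 min between orders; MIST onset differs by 61.5 − 55 = 6.5 min.

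**Other readings** (minutes after spray)

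| Assumption changed | Functional data |
|---|---|
| None (nominal) | 55-85.5 |
| 22-min MIST | 55-83.5 |
| Session means first functional run | 45-75.5 |
| Interval is 40 min | 50-80.5 |
| Neutral faces take 2 further task and 2 further rest blocks (assumed) | 55-87.5 |

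If the session means the first functional run, 5 of the 30.5 task minutes fall at 45-50 and 25.5 fall later. With a 40-minute interval, data begin at the upper edge of 45-50. Any positioning or mock-scanner time that falls after the 45 minutes, or any gap between tasks, moves task data later.

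**Precision of a treatment-by-order term**

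Assume 40 per arm, split evenly by order (20 per cell), with residual standard deviation σ.

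- Standard error of the treatment difference: σ√(2/40) = 0.22σ.
- Standard error of the difference in treatment effect between orders: σ√(4/20) = 0.45σ, twice as large.

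**The case against.** The strongest reply is that the plan never calls 45-50 minutes a window. It does not say that the response ends at 50 minutes, or whether the figure marks the start of scanning, the first task or the measurement itself. If the cited studies began scanning at that time, tying the spray to the session simply follows them. The documents cannot settle this. The reply defeats two stronger readings that a reader might infer: that the tasks are run after the drug effect has gone, and that a null result is built into the design. The plan gives no time course for the response, so no loss can be claimed or calculated.

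The procedures can also all be carried out together, so this is not an operational contradiction. Nor can it be said without qualification that every task block misses 45-50 minutes. That depends on the session starting at tuning, on the pictures spanning exactly the pre-task period, and on an approximate 45 minutes being 45. No ordering could fit a 24-minute task and a 6.5-minute task into five minutes.

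Counterbalancing is deliberate, and under blinded random assignment timing should not differ systematically between oxytocin and placebo. That makes the order effect mainly a matter of noise and interpretation rather than bias, although the plan does not say that order is balanced within treatment arm.

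What stands is that, on each reading examined, most or all task data are later than the time the plan cites, and that a known design factor is missing from the models.

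**Conclusion.** The point holds as a mismatch between the stated rationale and the schedule. Nominally, functional data fall at about 55-86 minutes after the spray. The plausible alternatives give about 45-76 minutes (session read as the first functional run) and about 50-81 minutes (40-minute interval). Face-task onset is about 24 minutes later when the MIST comes first, and neither order nor time since dose enters the 1B or 2B analysis.

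The ranges assume that the pictures are shown once and fill the pre-task period, and that there are no gaps between tasks. The documents do not support going further: they neither show a weaker oxytocin response at these times nor establish that the cited figure refers to task time. The matter should be corrected because the remedies are cheap and the randomised imaging hypotheses depend on it; it does not invalidate the design.

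**What to change.** 1. **Reconcile the text.** Medication Administration, MRI Data Acquisition and the two task sections should together state which event the spray interval refers to and how the resulting task times relate to the cited 45-50 minutes. The choice of dosing time stays with the sponsor; none is proposed here.
2. **Change the imaging order.** Keep tuning and localising first and acquire the T1 MPRAGE after both tasks. This recovers at most about 10 minutes, and less in practice, because the plan gives no separate durations for tuning, localising and MPRAGE. The downsides are a shorter settling period before the first task and no anatomical image for a participant who stops early, which section 2.2 allows at any time.
3. **Record times.** Log the clock time of the spray and of the onset of each task. The cost is a few entries per visit.
4. **Model order.** Include task order as a factor in the 1B and 2B models, at one degree of freedom each, and state whether order is balanced within treatment arm.
5. **Add a sensitivity analysis.** Fit a treatment-by-order term, or treatment by time since dose. An additive minutes covariate would not do, because it cannot show whether the oxytocin effect changes with time. Report the term as descriptive, given its doubled standard error. State that order and time since dose are nearly collinear, so a difference could not be separated from habituation. For participants already scanned, this is possible wherever order or clock times were kept.
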